9.6 Interim follow-up

An unscheduled interim follow-up may occur anytime during the course of the study. It is not required to document data on an eCRF. Only in the cases where adverse events occur this shall be documented on the AE-eCRF.

In case of BIOMONITOR III revision or replacement during study participation the following data shall be entered on the AE-eCRF:

- Reason for revision or replacement
- Revision/replacement procedure information (date of intervention, type of intervention, information about the new implanted devices)
- Insertion position for revised / replaced BIOMONITOR III

In case of BIOMONITOR III explantation during study participation the following data shall be entered on the AE-eCRF:

- Reason for explantation
- Explantation procedure information (date of intervention, type of intervention)
- Information about new device (e.g. pacemaker), if applicable.

Please note that explanted BIOMONITOR III devices must be returned to BIOTRONIK for analysis.

9.7 Device data read out

For the download of the device data read out (RAM-Dump), the following steps are required:

- Connect an USB flash drive to the Renamic with a storage capacity of at least 256 MByte.
- Apply the programming head above BIOMONITOR III.
- Download the data from the BIOMONITOR III memory while the patient is in a reclined position. Select the items as shown in Figure 13. The data transmission can take about 5 minutes. `More` → `BIOMONITOR III` → `Device Data` → `Read out`
- Please provide the USB flash drive to a BIOTRONIK employee or send the electronic data to the Center for Clinical Research of BIOTRONIK using the study email address [contact]

[figure not shown]

Figure 13: Device data read out

9.8 Termination and post treatment

The study termination eCRF must be completed to determine the end and reason for study termination of the individual patient. The regular termination of the patient is defined as the time when the 1-month Home Monitoring observation and telephone interview is completed. The frequency and elements of routine visits according to standard guidelines for ICM therapy are adequate for all patients after regular study termination.

In the case of patients who do not show up for the scheduled 1-week follow-up, all efforts should be made to contact them and complete the required checks, even if this would be far out of the planned schedule. Equally, all efforts should be made to contact the patient for the 1-month follow-up to assure that no adverse events will remain unnoticed. It should be kept in mind that the study device has no market approval and is implanted only under the condition that the patient is followed in this study.

Follow-up of subjects which have withdrawn consent is covered in section 8.3.5.1.

9.9 Description of those activities performed by sponsor representative

Sponsor representatives will support the investigator during insertion or follow-up procedures if this is part of the clinical routine. They might also support the investigator by programming the ICM. Nevertheless, the investigator and the trained study team are responsible for the adherence to the study protocol.

Monitoring will be performed by a sponsor representative according to the monitoring plan.

Qualified sponsor representatives from BIOTRONIK may support the investigator and study nurse in downloading and sending programmer data to CCR as part of their general technical assistance service.

9.10 Responsibilities

9.10.1 Responsibilities of the sponsor

The sponsor of the BIO|CONCEPT.BIOMONITOR III study is:

BIOTRONIK Australia Pty. Ltd.
[name]
[name]

[name]
Australia

Comprehensive responsibilities regarding study conduct and management are delegated to:

BIOTRONIK SE & Co. KG
Center for Clinical Research (CCR)
[name]
[name]
Germany

The sponsor and delegates ensure that all documents, information and necessary human resources are made available for initiation, conduct and termination of the study.

In addition, the sponsor and delegates are obliged to fulfill the following tasks (selection of items):

- Maintaining insurance cover or indemnification of subjects in case of injury in accordance with applicable laws.
- Contracting of investigational sites and investigators, specifically determining the agreement between sponsor and the research site with respect to such as but not limited to the following: conducting the contract research, obligations of the sponsor/the investigational site/the investigator, fee payments of the sponsor, intellectual property and publication of research results, confidentiality, insurance coverage and compliance with applicable laws/regulations and ethical standards. Selection of suitable investigational sites, investigators and clinical monitors.
- Obtaining of a favorable ethics vote(s) for conduct of the clinical study.
- Responsibility for all payments and financial coverage of the study, including patient travel reimbursement.
- Supervision of study conduct according to the legal regulatory requirements and the requirements of the CIP.
- Fulfill reporting duties of the sponsor to the ethic committees and regulatory authorities.
- Data analysis and data management.
- Performance of on-site audits as planned routine audits, on demand in case of detected non-compliances, or as preparation for an announced inspection by a Competent Authority.
- Provision of the final clinical investigation report (CIR) in accordance with applicable legal requirements and ethical principles.

9.10.1.1 Project management

The clinical project manager is responsible for the following (selected items):

- Development of the clinical investigation plan and possible amendments.
- Coordination of all study-related activities dedicated to the sponsor.
- Support of investigational sites during the study (obtaining ethic committee votes, etc.).
- Continuous information of investigational sites and clinical monitors on study progress.
- The clinical project manager is supported by other staff members of the sponsor (e.g. in-house clinical project associates, data assistants, data base managers).

In case of questions concerning the clinical investigation plan, used medical devices and regulatory requirements, the investigator should contact the clinical project manager.

9.10.1.2 Data Management

The data manager is responsible for the following items (selection of items):

- Development and maintenance of the clinical data management system (CDMS; iMedNet of the company MedNet Solutions Inc, Minnetonka, MN 55305 USA).
- Development of the data management plan.
- Development of the eCRF user guide.
- Data management.

9.10.1.3 Biostatistician

The statistician is responsible for the following items (selection of items):

- All statistical aspects within the clinical investigation plan.
- Statistical analysis for clinical investigation report.

The statistician will be supported by other staff members of the sponsor.

9.10.1.4 Monitor

The sponsor names clinical monitors for each participating investigational site prior to initiation of the respective site. Names and contact data will be provided to the investigational sites in due time. In case of changes, the investigational site will be informed by the sponsor. An adequate monitoring will be ensured by the sponsor. Monitoring will be conducted according to the SOPs of the sponsor. Responsibilities of the clinical monitors are described in section 10 of this document.

9.10.2 Responsibilities of the investigators

9.10.2.1 Coordinating Investigator

The clinical study BIO|Concept.BIOMONITOR III is coordinated by:

A/[name]
The Alfred Hospital
Department of Cardiology
[name]
[name]

The responsibilities of the Coordinating Investigator are listed in the following:

- Development and review of the clinical investigation plan.
- Procurement of the central vote of an ethics committee.
- Performance and progress control of the study.
- Continuous assessment of the risk/benefit ratio.
- If necessary, decision on premature study termination in consultation with the sponsor.
- Contribution to coordination of publication and presentations of study results.

- Advising all investigators in medical questions related to the study or study conduction.
- Evaluation of potential unexpected adverse events.
- Discussion of possible interim results.
- Cooperation in writing of the final clinical report.

The Coordinating Investigator is supported by the clinical Project Manager and other members of the sponsor.

In addition, the Coordinating Investigator has the same rights and duties as other principal investigators.

9.10.2.2 Investigator

The study shall be conducted by qualified investigators.

Rights and duties of the investigators are specified in the clinical investigation plan and are further regulated in the contract for study conduct. The principal investigator named in the study contract may share the rights and duties with investigators and other staff at the investigational sites. Nevertheless, the principal investigator retains the main responsibility for proper study conduct with respect to the following duties:

- Registration of the study to the bodies responsible for the investigational site (e.g. hospital administrative department).
- Notification to competent authority (if applicable) responsible for the investigational site.
- If required, obtaining of a positive vote of the ethics committee responsible for the investigational site.
- Adverse Event reporting according to the clinical investigation plan.
- Recruitment of suitable patients in an adequate time frame.
- Patient information and obtaining of written informed consent of the patient according to the requirements of the CIP.
- Safe and efficient use of devices.
- Inform the sponsor about new study team members before authorizing them for study related activities.
- Provide the sponsor with required documentation for assessing the qualification of study team members.
- Authorize co-investigators only after documented adequate study specific training.
- Discourage patients to consent for other interventional clinical investigations, in case the investigator is aware of such intentions beforehand. Inform the sponsor and follow the sponsor's guidance, in case a patient has already been enrolled into another interventional clinical investigation. Obtain the sponsors permission before enrolling the patient into another interventional clinical investigation.
- Conduct of the study according to the CIP.
- Data collection and data entry in accordance with the requirements of the CIP.
- Providing supporting material, if necessary.
- Submission of safety reports and protocol deviations to ethics committee and competent authorities (if applicable).
- Support of monitoring and auditing activities.
- Confidential treatment of all study-related documents and information.

In case the principal investigator (or authorized staff) does not fulfill the requirements defined, the sponsor is entitled to exclude the respective investigational site or principal investigator from further study participation.

9.11 Possible influencing factors on outcome or interpretation of results

No factors that could influence the outcome or interpretation of the results are known at this time.

10 MONITORING PLAN

The responsibility of BIOTRONIK as sponsor is to ensure protocol and regulatory compliance through proper monitoring of the study. BIOTRONIK is required to ensure that the BIOMONITOR III system is used under the immediate direction of an investigator. As the investigator, the physician is responsible for conducting the study in accordance with the signed the clinical investigation plan, applicable laws, local regulations and any conditions of approval imposed by the reviewing EC.

The entries in the eCRF will be reviewed and source data verified at the investigational site by monitors (authorized BIOTRONIK personnel, Clinical Research Associates-CRAs, or by authorized BIOTRONIK designees) to ensure that the investigator and the clinical investigation team conducts the clinical investigation in accordance with the CIP, The Declaration of Helsinki, ISO 14155, and applicable applicable laws and regulations to ensure adequate protection of the rights, safety and wellbeing of subjects and the quality and integrity of the resulting data.

A monitor will visit the study site periodically during the study. All actively enrolling sites will have at least an initiation visit, one early monitoring visit after the first patients have been enrolled in order to detect and prevent systematic errors in study conduct or documentation, and a close-out visit. Additional monitoring visits will be conducted based on risk related criteria such as e.g. recruitment rate and documentation quality. Details on criteria for initiating monitoring visits as well as strategy and extent of source data verification are subject to a detailed monitoring plan developed by BIOTRONIK as an internal document.

Monitoring visits will assure, amongst others, that the facilities are still acceptable, that the CIP is being followed, that the EC has been informed about approved CIP changes as required, that records on study conduct and data collection are complete and present, that appropriate and timely reports have been made to the sponsor and the authorities, and that the investigator is carrying out all agreed activities.

Assessments of the study site will include but will not be limited to the following:

1. Completion and submission of the required electronic case report forms (eCRFs) and other applicable study documentation
2. Continued acceptability of the facilities, including storage and maintenance of investigational inventory
3. Adherence to the clinical investigation plan
4. Adherence to current version of ISO 14155 and applicable local regulations and laws

If a monitor becomes aware that an investigator is not complying with the requirements mentioned above, the monitor is obliged to notify BIOTRONIK study management. BIOTRONIK will evaluate the non-compliance and issue corrective actions, discontinue enrollment or as a last measure close the clinical investigational site (see sections 14 and 20).

11 STATISTICAL CONSIDERATIONS

11.1 Statistical design, method and analytical procedures

The BIO|CONCEPT.BIOMONITOR III study is designed as an open-label, prospective, non-randomized, multicenter one-armed, international study.

For continuous variables, descriptive statistics (mean, median, standard deviation, first and third quartile, minimum and maximum) will be calculated. For categorical variables absolute and relative frequencies (based on the number of non-missing data) will be calculated.

For selected variables two-sided 95% confidence intervals for the respective parameters will be given.

11.2 Sample size

Since no hypothesis will be assessed, no formal sample size calculation based on standard statistical methods can be done.

Instead, the sample size of this study has been deduced following the method proposed by Viechtbauer et al.⁵⁷. A sample size of 45 patients would allow with 95% confidence to observe at least one event of a certain type of events if this type of events would occur with 15% probability in the respective population.

This is not to implicate that a rate of 15% of a certain type of events is expected; it merely means that if unforeseen risks existed at such a high rate, one might be 95% confident to observe at least one such event in the study and measures could be taken before market introduction.

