8.1.6 Replacement of subjects

Patients who drop-out before insertion will be replaced. Therefore it is possible that more than 45 patients are enrolled in order to get data from 45 insertions.

8.2 **Used devices and comparators**

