11.4 Expected drop-out rate

The drop-out rate is expected to be < 10 %.

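### Protocol 11.2: 45 patients, 95% confidence and a 15% event rate do not fit together; at 95% confidence, 45 patients correspond to a rate of about 6.5%

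*Protocol*

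**What the plan says.** Section 11.2 first explains why there is no conventional calculation: "Since no hypothesis will be assessed, no formal sample size calculation based on standard statistical methods can be done". It then says that the size was derived by a published pilot-study method, cited as reference 57, and gives the result: "A sample size of 45 patients would allow with 95% confidence to observe at least one event of a certain type of events", with the condition "if this type of events would occur with 15% probability in the respective population".

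The next paragraph adds that 15% is not an expected rate. It describes 15% as a high rate and says that, if unforeseen risks existed at that level, "one might be 95% confident to observe at least one such event in the study and measures could be taken before market introduction". The 15% and the 95% therefore each appear twice, with the same meaning both times.

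No other section gives a numerical basis for 45. Section 5.3 supports up to 45 patients and about 15 investigators by the first clinical use of the device. Sections 8.1.2 and 11.13 explain the spread over many operators and the limit of 5 per investigator. Section 8.2.4 deals with device supply. Section 11.3 states that no power can be defined.

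**The concern.** The method described is the zero-event binomial argument, in which any two of sample size, confidence and event rate fix the third. The section gives all three, and they do not agree.

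The figure describes what the study can detect. Section 4.8 says that the device has never been inserted in a living person. Section 11.2 ties its figure to measures taken before market introduction, and section 11.6 plans an interim analysis to support the launch decision. The highest quantified class in Table 3 (section 18.7) is 1 to 10 patients per 100. A rate of 15% lies above that whole class, whereas about 6.5% lies inside it. A reader who takes 15% as the rate matched to 95% confidence gets a materially wrong picture of the study's sensitivity to events of the kind the protocol itself lists.

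The calculation cannot be recovered from its source either. Entry 57 in section 22 is a paper on how often to monitor for recurrence of atrial fibrillation, and no entry in the list matches the method named in 11.2.

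**Working it through.** **Inputs, all from section 11.2:** n = 45 patients; confidence of at least one event = 95%; event probability per patient p = 15%.

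**Formula.** For independent patients with a common event probability p:

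- P(at least one event) = 1 − (1 − p)^n
- n = ln(1 − confidence) / ln(1 − p)
- p = 1 − (1 − confidence)^(1/n)

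**Attempt to reproduce 45 from 95% and 15%.** n = ln(0.05) / ln(0.85) = 18.43, so 19 patients. Check: 1 − 0.85^19 = 95.4%. The stated 45 is not reproduced; it is 45/19 = 2.4 times the number needed.

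**Keep 45 and 15%, solve for confidence.** 1 − 0.85^45 = 99.93%, not 95%.

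**Keep 45 and 95%, solve for the rate.** p = 1 − 0.05^(1/45) = 6.44%, not 15%. The ratio is 15/6.44 = 2.3. The rule of three gives nearly the same: 3/45 = 6.7%.

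**Could another reading give 45?** All of these use p = 15%:

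| Variant | n needed | Fits the text? |
|---|---|---|
| 95%, at least one event | 19 | Yes, but is not 45 |
| Same, inflated for 10% drop-out | 22 (divide by 0.90) or 21 (multiply by 1.10) | Not 45 |
| 97.5%, at least one | 23 | Not 45; contradicts 95% |
| 99%, at least one | 29 | Not 45; contradicts 95% |
| 99.9%, at least one | 43 | Near 45; contradicts 95%, stated twice |
| 95%, at least three events | 40 | Not 45; contradicts at least one |
| 95%, at least four events | 50 | Not 45; contradicts at least one |

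No variant that keeps the section's own terms gives 45.

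**Rounding for the restatement.** At exactly 6.4%, 1 − 0.936^45 = 94.9%, just short of 95%. At 6.5%, 1 − 0.935^45 = 95.1%. A statement promising at least 95% should therefore use 6.5%.

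**The case against.** The strongest reply is that the sentence is true as a guarantee. At a 15% rate, 45 patients give 99.93%, which is more than 95%. The error understates what the study can detect, so no one is promised more than the study delivers. The study is also exploratory, with no hypotheses, power or pass/fail criteria, and no analysis or decision rule uses the 15%. All of this stands, and it limits the seriousness of the point. It does not rescue the claim that 45 was derived from these inputs.

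Three stronger readings are tempting but are not supported.

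- **That readers are told only risks of 15% or more would be seen.** Section 11.2 does not say this. It says what would happen if risks existed at that rate and does not deny that rarer events could appear. Nor does it claim that the study excludes any rate.
- **That the figure is undermined by drop-out.** Section 11.4 expects less than 10%, but section 8.1.6 states "Patients who drop-out before insertion will be replaced", with the aim of data from 45 insertions. Section 8.3.4.1 bars investigators from excluding a patient once insertion has been attempted. Section 5.3 expects insertion-related events within the first days, and section 8.3.4.3 allows earlier data to be kept after withdrawal if consent to data processing stands. Most patients lost later would therefore still contribute. Even with 41 patients, 1 − 0.85^41 = 99.9%.
- **That 19 patients would have been enough, or that 11.2 is the sole reason for 45.** It is the sole quantitative reason. The aim of having many operators assess the insertion tools is a separate ground for a larger number, and nothing in the protocol proposes a smaller study.

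It is also fair to say that the document does not show which figure is the slip. Three sets are consistent: 45 with 95% and about 6.4%; 19 with 95% and 15%; and 45 with 99.9% and 15%.

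**Conclusion.** The inconsistency is real and can be checked from section 11.2 alone. At 95% confidence, 45 patients correspond to an event rate of 6.44%, so the stated 15% is too high by a factor of about 2.3. Equivalently, the confidence at 15% is 99.9%, and 95% at 15% needs only 19 patients. The direction is conservative: the study is not undersized for its stated aim, and the fault lies in the rationale, not in the number enrolled. The point still deserves correction because this is the only numerical justification of the size of a first-in-human study and its cited source cannot be found in the reference list.

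The figures assume independent patients with one common event probability and 45 insertions that contribute data. Section 11.2 states no other model, and in particular makes no allowance for correlation between patients treated by the same investigator.

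**What to change.** The sponsor should confirm which of the three figures was meant and restate section 11.2 accordingly. If 45 and 95% are the intended figures, suitable wording would be:

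> With 45 insertions, the probability of observing at least one event is at least 95% for any event type with a true rate of 6.5% or more (99.9% at a rate of 15%).

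The following paragraph, which repeats the 15% and describes it as high, should be changed to match. Reference 57 should be replaced by the source of the method, and that source added to section 22.

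The cost is one reworded passage and one corrected citation. Enrolment, procedures and analyses do not change.

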11.3 Level of significance and the power of the study

A p-value of less than 0.05 will be considered to indicate statistical significance for any comparison. Since no hypotheses are specified, no power can be defined.

11.4 Expected drop-out rate

The drop-out rate is expected to be < 10 %.

11.5 Pass/fail criteria

Not applicable.

11.6 Provision for an interim analysis

An interim analysis is planned in June 2019. All available data will be analyzed to support the management decision regarding product launch of the BIOMONITOR III. Additionally, it could be necessary to run preliminary ad hoc analyses. If so, no bias is expected because no hypotheses are defined.

